8.3.3.3 Expectedness

An AE will be considered unexpected if the nature, severity, or frequency of the event is not consistent with the risk information previously described for the study intervention.

8.3.4 Time Period and Frequency for Event Assessment and Follow-up

The occurrence of an adverse event (AE) or serious adverse event (SAE) may come to the attention of study personnel during study visits and interviews of a study participant presenting for medical care, or upon review by a study monitor.

All AEs including local and systemic reactions not meeting the criteria for SAEs will be captured on the appropriate case report form (CRF). Information to be collected includes event description, time of onset, clinician's assessment of severity, relationship to study product (assessed only by those with the training and authority to make a diagnosis), and time of resolution/stabilization of the event. All AEs occurring while on study must be documented appropriately regardless of relationship. All AEs will be followed to adequate resolution.

Any medical condition that is present at the time that the participant is screened will be considered as baseline and not reported as an AE. However, if the study participant's condition deteriorates at any time during the study, it will be recorded as an AE.

Changes in the severity of an AE will be documented to allow an assessment of the duration of the event at each level of severity to be performed. AEs characterized as intermittent require documentation of onset and duration of each episode.

All reportable events will be recorded with start dates occurring any time after informed consent is obtained until 7 (for non-serious AEs) or 30 days (for SAEs) after the last day of study participation. At each study visit, the investigator will inquire about the occurrence of AE/SAEs since the last visit. Events will be followed for outcome information until resolution or stabilization.

8.3.5 Adverse Event Reporting

An independent Data Safety Monitoring Board (DSMB) will be utilized during the study. The DSMB will consist of 2 Board Certified Allergy/Immunology physicians who are not participating in the study and do not have any conflicts of interest as well as 1 pediatric physician of another specialty. The DSMB will meet prior to initiation of the study, following the enrollment of the 6th subject, and then quarterly during the course of the study.

8.3.6 Serious Adverse Event Reporting

The study clinician will immediately report to the sponsor any serious adverse event, whether or not considered study intervention related, including those listed in the protocol or investigator brochure and must include an assessment of whether there is a reasonable possibility that the study intervention caused the event. Study endpoints that are serious adverse events (e.g., all-cause mortality) must be reported in accordance with the protocol unless there is evidence suggesting a causal relationship between the study intervention and the event (e.g., death from anaphylaxis). In that case, the investigator must immediately report the event to the sponsor.

All serious adverse events (SAEs) will be followed until satisfactory resolution or until the site investigator deems the event to be chronic or the participant is stable. Other supporting documentation of the event may be requested by the study sponsor and should be provided as soon as possible.

The study sponsor is responsible for notifying the Food and Drug Administration (FDA) of any unexpected fatal or life-threatening suspected adverse reaction as soon as possible, but in no case later than 7 calendar days after the sponsor's initial receipt of the information. In addition, the sponsor must notify FDA and all participating investigators in an Investigational New Drug (IND) safety report of potential serious risks, from clinical trials or any other source, as soon as possible, but in no case later than 15 calendar days after the sponsor determines that the information qualifies for reporting.

8.3.7 Reporting Events to Participants

All anticipated AEs will involve overt symptoms and thus be readily apparent to the subjects and their families. When an AE occurs during a study visit, the nature and severity of the AE as well as the implications for ongoing treatment will be discussed by a physician investigator with the subject and parents/guardians. This discussion will take place after any potential treatment is administered and the subject is deemed medically stable but prior to end of the study visit.

When an AE occurs at home, the nature and severity of the AE as well as the implications for ongoing treatment will be discussed by a physician investigator with the subject and parents/guardians via phone. If a study visit is deemed appropriate to further manage the AE or for further discussion of the AE, then additional discussion will take place at this time.

8.3.8 Events of Special Interest

This is not applicable to our study.

8.3.9 Reporting of Pregnancy

If a pregnancy were to occur during the course of the study, the subject would be withdrawn from the study. The pregnancy would be reported to the PRRC and IRB at the Cleveland Clinic. The subject would be referred to an appropriate physician (OB/Gyn) for further management.

8.4 Unanticipated Problems

8.4.1 Definition of Unanticipated Problems (UP)

The Office for Human Research Protections (OHRP) considers unanticipated problems involving risks to participants or others to include, in general, any incident, experience, or outcome that meets all of the following criteria:

- Unexpected in terms of nature, severity, or frequency given (a) the research procedures that are described in the protocol-related documents, such as the Institutional Review Board (IRB)-approved research protocol and informed consent document; and (b) the characteristics of the participant population being studied;
- Related or possibly related to participation in the research (“possibly related” means there is a reasonable possibility that the incident, experience, or outcome may have been caused by the procedures involved in the research); and
- Suggests that the research places participants or others at a greater risk of harm (including physical, psychological, economic, or social harm) than was previously known or recognized.

8.4.2 Unanticipated Problem Reporting

The investigator will report unanticipated problems (UPs) to the reviewing Institutional Review Board (IRB) and to the lead principal investigator (PI). The UP report will include the following information:

- Protocol identifying information: protocol title and number, PI's name, and the IRB project number;
- A detailed description of the event, incident, experience, or outcome;
- An explanation of the basis for determining that the event, incident, experience, or outcome represents an UP;
- A description of any changes to the protocol or other corrective actions that have been taken or are proposed in response to the UP.

To satisfy the requirement for prompt reporting, UPs will be reported using the following timeline:

- UPs that have serious impact or require a change to the protocol will be reported to the IRB and to the study sponsor within 10 days of the investigator becoming aware of the event.

- All UPs should be reported to appropriate institutional officials (as required by an institution's written reporting procedures), the supporting agency head (or designee), and the Office for Human Research Protections (OHRP). The reporting timeline for UPs that do not have serious impact or require a change to the protocol will be the time of continuing renewal with the IRB.

8.4.3 Reporting Unanticipated Problems to Participants

Should unanticipated problems arise that have serious impact to the protocol or to the safety of participants, participants will be notified based on the opinion of the IRB once the UP has been reviewed.

9. Statistical Considerations

9.1 Statistical Hypothesis

We will obtain observation data on patients receiving boiled peanut oral immunotherapy which has not yet been well described in human trials. We will compare with proportion of patients successfully desensitized as defined by meeting the primary endpoint with the expected placebo rate. The null hypothesis is that the proportion of patients successfully desensitized by boiled peanut oral immunotherapy will not be greater than the expected 20% that has been previously published as the proportion of patients successfully meeting the primary endpoint in OIT studies (which aligns with the expected 20% that would naturally "outgrow" a peanut allergy). If we reject this null hypothesis, we will be able to conclude that the proportion of successfully desensitized by boiled peanut therapy is greater than placebo. For the safety aspect of the study we will be comparing the historical SAEs/AEs of patients who received OIT with roasted peanuts and compare them with the patients enrolled in this study for the rate of occurrence and severity of the SAEs/AEs observed.

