A commercially developed product, AR101 (Aimmune Therapeutics), an investigational oral biologic drug, was recently trialed in a phase 3 study evaluating efficacy. In the intervention group, 67.2% of patients ages 4–17 tolerated at least a 600-mg dose of peanut protein in the exit food challenge, compared to 4.0% of placebo patients ($p < 0.00001$). In the trial's primary analysis group of ages 4–17, 496 patients from both arms (372 AR101 and 124 placebo) were evaluable for safety. In both arms, the incidence of serious adverse events (SAEs) was low. A total of 10 patients experienced SAEs, none of which were considered life-threatening: nine of these patients were in the AR101 arm (2.4%) and one was in the placebo arm (0.8%). Of the nine AR101 patients who experienced a SAE, five patients experienced mild or moderate SAEs. The other four AR101 patients experienced severe SAEs, which, for two of these patients, were not related to treatment (a concussion and a viral asthmatic exacerbation). Of the two patients who experienced severe SAEs related to treatment, both of whom had elevated baseline peanut-specific IgE levels greater than 100 kU/L, one experienced anaphylaxis, and the other experienced wheezing on the first day of treatment. Both of these patients discontinued from the study. In ages 4–17, 20.4% of AR101 patients and 6.5% of placebo patients discontinued the trial. In the AR101 arm, 12.4% of patients discontinued due to investigator-reported adverse events, including 6.7% due to gastrointestinal adverse events and 2.7% due to systemic allergic hypersensitivity reactions. In the placebo arm, 2.4% of patients discontinued due to investigator-reported adverse events (Table 2).²⁸

Table 2: Discontinuations in the AR101 Group²⁸

	AR101 (n= 372)	
	%	n
Total discontinuations regardless of causality	20.4%	76
Discontinuations not related to adverse events	8.0%	30
Discontinuations related to adverse events	12.4%	46
• Gastrointestinal ²	6.7%	25
• Systemic hypersensitivity reactions ³	2.7%	10
• Respiratory system	1.1%	4
• Cutaneous	0.8%	3
• Other	1.1%	4

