+105 minutes	4000mg	Examination of skin and auscultation of lungs prior to dose Full physical examination of ears, oropharynx and nose, lungs, and skin after completion of final dose.

*Vital signs including heart rate, blood pressure, respiratory rate and oxygen saturation level to be obtained with any change in physical exam or clinical status

If objective signs of an allergic reaction occur, then the challenge will be stopped, and the subject treated based on the presenting symptoms and clinical judgment of the supervising investigator (Table 4). If no objective signs occur within 2 hours after the last dose is consumed, then the child will be considered not peanut allergic and will not qualify for the study.

Table 4: Oral food challenge stopping criteria

A positive food challenge will be defined by the presence of either of the following:
 
 • One or more major criteria • Two or more minor criteria 
An indeterminate food challenge will be defined by the presence of one minor criterion.
 
A negative food challenge will be defined by the absence of major or minor criteria.
 
All symptoms should be of new onset and not due to ongoing disease. Symptoms must occur no later than 2 hours after the last dose.

Major Criteria

 • Confluent erythematous pruritic rash • Respiratory signs (at least one of the following): 
 Wheezing Inability to speak Stridor Dysphonia Aphonia • $>/= 3$ noncontact urticarial lesions lasting for more than 3 minutes • $>/= 1$ site of angioedema • Hypotension for age not associated with vasovagal episode • Evidence of severe abdominal pain (such as abnormal stillness or doubling over) that persists for more than 3 minutes
Minor Criteria

 • Vomiting (persistent symptoms would elevate to major criterion) • Diarrhea • Persistent rubbing of nose or eyes that lasts for $>/= 3$ minutes • Persistent rhinorrhea that lasts for $>/= 3$ minutes • Persistent scratching that lasts for $>/= 3$ minutes

The subjects with objective signs of an IgE mediated reaction to peanut using standard criteria (Table 4) will be eligible for enrollment.

If patient is found to be study eligible, then a urine pregnancy test will be done on females who have reached the age of child birthing potential.

Initial Dose Escalation

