9.2 Sample Size Determination

The sample of 10 patients will provide >90% power to determine the expected success rate (80%) is greater than a theoretical placebo rate (20%).

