9.4 Statistical Analysis

Descriptive statistics will be used to summarize the data. Categorical variables will be presented as number and percentage of total patients. Continuous variables will be summarized using mean, standard deviation, median and [Q1, Q3]. The proportion of patients with successful consumption of peanut protein without symptoms (primary endpoint), will be tested to determine whether the proportion differs from 0.2 (20%) (the expected success rate in a theoretical placebo group).

10. Supporting Documentation and Operational Considerations

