6.3.3 Assessment of Safety Endpoints

AEs, including Serious Adverse Events (SAEs) will be graded according to severity using the Consortium of Food Allergy Research (CoFAR) scale, which is 5-point ordered scale from mild (1) to death (5). AEs will be categorized by preferred term using the Common Terminology Criteria for Adverse Events (CTCAE) Version 5.0 and for the specific AEs for interest listed in section 5.2, by treatment required, and by study phase (dose escalation study visits, home doses, exit DBPCFC, and overall).

7 Sample Size

We will compare with proportion of patients successfully desensitized as defined by meeting the primary endpoint with the expected placebo rate. The null hypothesis is that the proportion of patients successfully desensitized by boiled peanut oral immunotherapy will not be greater than the expected 20% that has been previously published as the proportion of patients successfully meeting the primary endpoint in OIT studies (which aligns with the expected 20% that would naturally “outgrow” a peanut allergy). If we reject this null hypothesis, we will be able to conclude that the proportion of successfully desensitized by boiled peanut therapy is greater than placebo. The sample of 10 patients will provide >90% power to determine the expected success rate (80%) is greater than a theoretical placebo rate (20%).

8 General Analysis Considerations

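### Rejecting the fixed 20% null shows only that the response rate exceeds 20%; Protocol 9.1 and SAP 7 instead draw a conclusion about placebo that a single-arm trial cannot support

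*Protocol*

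**What the plan says.** Protocol 9.1 sets the null hypothesis that the proportion desensitized is not "greater than the expected 20% that has been previously published as the proportion of patients successfully meeting the primary endpoint in OIT studies". A parenthesis adds a second support, "which aligns with the expected 20% that would naturally" outgrow the allergy. On rejection, the protocol states, "we will be able to conclude that the proportion of successfully desensitized by boiled peanut therapy is greater than placebo". SAP 7 repeats all of this.

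Elsewhere the label is weaker. Protocol 9.4 calls 20% "the expected success rate in a theoretical placebo group", and the synopsis, Protocol 9.2 and the last sentence of SAP 7 also use the word *theoretical*. SAP 6.1 describes a single-arm study without randomization or blinding. SAP 10.1 specifies an exact one-sided test at 0.05 against 20%, with missing outcomes counted as non-response. Placebo appears in Protocol 6.1.2 only as oat flour for the exit challenge, not as a treatment.

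The only exit-challenge success rates printed are in Protocol 2.2, from the phase 3 trial of a commercial peanut product in ages 4-17: 67.2% on active treatment, "compared to 4.0% of placebo patients", both at 600 mg or more. This trial's endpoint is a single dose of 300 mg or more.

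**The concern.** The interpretive sentence turns a comparison with a constant into a comparison with placebo. That step is valid only if 20% is the rate at which these children would pass the exit challenge untreated. The trial does not measure that rate, and the documents do not establish it.

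What is at stake is the claim the trial may make. A positive result reported in the words of Protocol 9.1 would say more than the design can show. A reader also could not tell whether 20% is a strict or a lenient hurdle for this endpoint and this entry rule.

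**Working it through.** **1. The plan's own figure.** Inputs: n = 10, null 20%, expected rate 80% (Protocol 9.2); exact one-sided 0.05 (SAP 10.1). With X responders,

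P(X ≥ r) = Σ C(10,k) p^k (1−p)^(10−k), summed over k = r to 10.

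At p = 0.20 and r = 5 the terms are 0.02642 + 0.00551 + 0.00079 + 0.00007 + less than 0.00001 = 0.0328. At r = 4 the sum is 0.1209. The test therefore rejects at 5 or more of 10. The one-sided 95% Clopper-Pearson lower bound is 22.2% at 5/10 and 15.0% at 4/10, so the confidence-bound rule agrees with the test. Power at 80% is P(X ≥ 5 | p = 0.8) = 0.994. The stated power above 90% is reproduced.

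**2. What rejection shows.** The hypothesis tested is p ≤ 0.20 in treated children. Its rejection bounds p and nothing else. With no untreated group, no placebo rate is estimated.

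**3. The published-rate sentence.** It can be read in two ways.

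- *Literally*, "expected 20% that has been previously published as the proportion of patients successfully meeting the primary endpoint in OIT studies" is a success rate for OIT. The printed active rate is 67.2% at 600 mg. A child who tolerates 600 mg in an ascending challenge has also tolerated 300 mg, so that arm's rate at 300 mg is at least 67.2%. The literal reading conflicts with Protocol 2.2.
- *As a placebo rate*, no citation stands beside it. By the same argument, the printed 4.0% at 600 mg is a lower bound for that trial's placebo rate at 300 mg. It neither supports 20% nor rules it out.

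**4. The outgrowing parenthesis.** The entry challenge goes to 4000 mg. If no objective signs follow, "then the child will be considered not peanut allergic and will not qualify for the study". Children who have already outgrown the allergy are thus removed, and planned exit is 18 weeks after that challenge (SAP 6.3). No time frame is given for the 20% who outgrow. A general outgrowing fraction is a poor match for the untreated pass rate here.

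**5. Why the untreated rate could also exceed 20%.** The upper entry steps are 100, 500, 1000 and 4000 mg (Protocol Table 3). A child who tolerates 500 or 1000 mg and reacts at a later step is eligible, yet has already taken a single dose above 300 mg. The cumulative dose points the same way in the SAP 6.3.2 table. Through 500 mg at entry it is 5 + 10 + 25 + 50 + 100 + 500 = 690 mg. Through 300 mg at exit it is 25 + 100 + 200 + 300 = 625 mg. The documents give no figure for the share of such children.

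**6. Consequence.** The chance that the planned rule (5 or more of 10) is met when treatment does nothing, by assumed untreated rate:

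| Assumed untreated rate | P(X ≥ 5) |
|---|---|
| 4% | 0.00002 (0.002%) |
| 20% | 0.033 (3.3%) |
| 30% | 0.150 (15.0%) |
| 40% | 0.367 (36.7%) |

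The 4% row uses the 600 mg figure as if it applied at 300 mg. The 30% and 40% rows are assumptions, not document figures.

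**The case against.** The best defence is that the operative analysis is sound. SAP 10.1 never mentions placebo; it tests whether the proportion exceeds 20%. SAP 6.1 calls 20% a null rate, and the word *theoretical* elsewhere tells readers there is no concurrent arm. The study is labelled proof of concept. This stands, and it limits the fault to justification and interpretation. It does not remove the sentence in Protocol 9.1 and SAP 7, which states what rejection will mean and omits that qualifier.

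A reader might also infer several stronger points that the documents do not support.

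- *That the printed 4.0% contradicts 20%, which is then five times too high.* In context, 20% is most naturally meant as a placebo rate. The ratio 20/4.0 compares rates at different thresholds, and 4.0% is only a lower bound at 300 mg.
- *That 20% comes from no matching placebo arm.* This cannot be checked. The documents cite trials whose placebo pass rates they do not print, and part of the reference list is not in the text available. What can be said is that no source is cited beside the figure.
- *That outgrowing is offered as the source of the 20%.* The text says only that it aligns. The entry challenge excludes allergy already outgrown, not resolution during the study, and SAP 6.3 sets no limits on visit timing, so 18 weeks is nominal.
- *That the type I error is inflated.* Against 20% it is 3.3%, below 5%. If the untreated rate were near 4%, the test would be very conservative. The higher rows of the table rest on assumed rates.

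**Conclusion.** The concern holds as a fault of inference and justification. The pre-specified conclusion about placebo does not follow from a single-arm test against a constant. The support for 20% is inadequate on either reading of the provenance sentence: the literal one conflicts with the 67.2% active rate, and the placebo one is unsupported rather than disproved.

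As evidence against placebo, the test has an error rate that depends on an unmeasured quantity: from 0.002% to 36.7% over assumed untreated rates of 4% to 40%. The direction is unknown, because the entry rule removes children who tolerate the whole challenge but admits some who already exceed 300 mg. These figures assume ten independent children with a common response probability, all with an observed outcome. The exact test, its level, the sample size and the stated power are not at fault.

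**What to change.** In Protocol 9.1 and SAP 7:

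- Replace the conclusion with: *the proportion exceeds a pre-specified fixed benchmark of 20%; no concurrent placebo comparison is made.*
- Reword the provenance sentence to say that 20% is an assumed benchmark. Add a source matched to the 300 mg endpoint and the entry rule if one exists.
- Drop the outgrowing parenthesis.
- Do not present 4.0% at 600 mg as the matching placebo rate; that would suggest a strict benchmark, which the entry rule does not guarantee.

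In reporting, state beside the primary result how many children already tolerated a single dose of at least 300 mg at the entry challenge. On the entry dose steps, this means a highest tolerated dose of 500 or 1000 mg. SAP Table 2.2 already lists challenge results by patient, so no new data are needed.

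Keep the test, alpha and N unchanged. The cost is wording, one added count and a more modest headline claim.
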